## SCHEMA

This Phase II study will investigate the utility of [ $^{18}\text{F}$ ] FMISO in patients with hepatocellular carcinoma (HCC). This trial is designed to test the hypothesis that PET determined [ $^{18}\text{F}$ ]FMISO uptake will indicate tumor hypoxia in patients with HCC treated with trans-arterial chemo-embolization (TACE). We anticipate that [ $^{18}\text{F}$ ] FMISO PET/CT will advance our understanding of the role of hypoxia in HCC prior to treatment and that this knowledge will help design newer combination therapeutic trials for better treatment outcomes.

Adults with HCC and limited hepatic disease eligible for TACE will be enrolled in the study and imaged according to the following schema: After imaging (FMISO 1 and FMISO 2 in the diagram below), patients will be followed for two years or until disease progression. [ $^{18}\text{F}$ ] FMISO PET/CT provides three parameters, tissue hypoxic volume (HV), maximum tissue to blood uptake ratio ( $T:B_{\text{max}}$ ) and tumor blood flow. Both pre-and post-therapy images will be examined to investigate changes in these parameters during the course of TACE treatment.

The study schema is shown below.

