**Figure 1.**

**Figure 1:** Diagram of patient management and timepoints where the [F] FMISO studies will be done in the course of treatment. FMISO PET #1 will be performed prior to treatment. FMISO PET #2 will be performed 1 month after all TACE procedures (in case multiple TACE procedures are performed) and prior to SBRT, and FMISO PET #3 will be performed 1 month following the end of liver stereotactic radiation therapy. 20 patients will be enrolled in this study.

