#### **2.1.a Role of Hypoxia in tumor proliferation and treatment responses of HCC**

Rapidly proliferating solid tumors are under-perfused at the central zone due to micro-environment changes and abnormal angiogenesis. These hypoxic areas derive oxygen predominately through the process of diffusion, which is often insufficient. Tumor cells surviving within hypoxic zones are therefore capable of anaerobic metabolism or other adaptive survival mechanisms. Preferential proliferation of cells adapted to hypoxia can thus result in increasing volumes of hypoxia within a growing solid tumor. Tumor hypoxia is a known prognostic indicator of response to anticancer treatments. Hypoxic cells are classically more resistant to radiation (RT).

In HCC, hypoxia is a significant contributor of tumor progression and treatment resistance. HIF-1 $\alpha$  levels are significantly elevated in HCC and act as the trigger for a number of down-stream events leading to tumor progression, invasion and metastases. Furthermore, hypoxia induced HIF-1 promotes gene expression that enhances cell survival under hypoxic conditions. In addition, it is also known that RT responses are enhanced in tumors deficient in the function of hypoxia-inducible factor-1. As with many other cancers, treatment planning can be tailored and intensified if tissue markers can be used to identify a patient at higher risk for treatment failure and poor outcome. PET imaging with a hypoxia specific imaging agent (FMISO) will be an effective means of identifying at risk HCC patients, and will provide critical information for combination treatment planning.

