The exploratory endpoints analysis include using cox regression analysis to correlate [F]FMISO parameters with overall survival and progression free survival; and using logistics regression analysis to associate [F]FMISO parameters with clinical response (yes, no). Baseline [F]FMISO, FU [F]FMISO, and changes of [F]FMISO between baseline and FU will be used individually in order to identify if early image of [F]FMISO at baseline, and treatment with TACE alone (FU1) and with radiation (FU2) can predict survival or response. Survival is defined from the time of initial PET scan to the last follow up. Patient's demographics and other prognosis factors will be adjusted in the model. The set of prognostic variables considered in the analysis include standard clinical measures (age, tumor-node-metastasis status), as well as the PET measurements [HV, and FMISO tissue to blood ratio (T/Bmax)]. Due to the high correlation between HV and T/Bmax, and the resulting issue of multicollinearity, these variables will each considered separately with the other prognostic variables. Hazard ratio and Odds ratio will be estimated along with 95% CI. Log-rank tests will be used to compare Kaplan-Meier survival curves associated with patients above and below the median values for the variables of interest. Survival curves are presented with time measured in months. It is important to notice that patient survival will be evaluated every six month through medical record, therefore the Interval-censored survival analysis will be applied which simply extends the approach used for right-censored observations to left- and interval-censored observations (Sun 2006). The probability of a left-censored time is the probability that the true time is less than or equal to the censoring time. And, the probability of an interval-censored observation is the probability that the true time is less than or equal to the upper bound of the interval minus the probability that the true time is less than or equal to the lower bound of the interval. The SAS procedure NPMLE could be used. In addition, we will estimate the optimal cut point of [F] FMISO level using

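### Section 7.3 times survival from the initial PET but uses later-scan values as predictors, with no landmark; the main risk is to the exploratory PFS analysis, and it is conditional and minor

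*Combined protocol and SAP*

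**What the plan says.** The exploratory part of section 7.3 correlates FMISO parameters with OS and PFS by Cox regression. Baseline, follow-up and change values are each used individually, to learn whether the baseline image and "treatment with TACE alone (FU1) and with radiation (FU2) can predict survival or response". Log-rank tests are to "compare Kaplan-Meier survival curves associated with patients above and below the median values for the variables of interest". The only origin given is in the sentence "Survival is defined from the time of initial PET scan to the last follow up"; PFS has no separate one.

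The figure legend in the schema puts scan 1 before treatment. For the second scan it states "FMISO PET #2 will be performed 1 month after all TACE procedures (in case multiple TACE procedures are performed) and prior to SBRT". The third scan is placed one month after radiotherapy is complete.

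On follow-up, the schema says "patients will be followed for two years or until disease progression". That sentence starts from the end of imaging and names only the first two scans. Section 7.3 adds that "patient survival will be evaluated every six month through medical record" and therefore plans interval-censored methods. Sections 7.1 to 7.4 contain no landmark, delayed entry, time-dependent covariate or rule for a patient who dies or progresses before scan 2 or scan 3.

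**The concern.** A scan-2 or scan-3 value does not exist at the time origin. Only patients who reach the scan have one, so their follow-up starts with a period that was event-free by selection, or, for PFS, a period in which the event may already have happened.

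PFS is the more serious case, because a patient can be alive but already progressed when scanned. The protocol's background gives a reason why progression could raise the value: "Preferential proliferation of cells adapted to hypoxia can thus result in increasing volumes of hypoxia within a growing solid tumor". Section 7.1 also counts metastases in the hypoxic volume. A tumor that has already progressed could then look like a scan that predicts progression. That would be a false lead in an analysis meant to supply hypotheses for later studies.

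**Working it through.** **The plan's own figures.** The plan states no event count, hazard ratio or power for the survival analyses, so there is nothing to reproduce on this point. Its one precision figure, the 0.448 interval width in 7.2, does reproduce (exact interval for 12/20: 0.361 to 0.809) but does not bear on it.

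**Minimum lags (schema figure legend).** Scan 1 precedes TACE, and scan 2 is 1 month after the last TACE, so the lag L is at least 1 month. SBRT follows scan 2, and scan 3 is 1 month after SBRT ends, so L is at least 1 + 1 = 2 months. No upper limit is stated and TACE may be repeated. Lags of 4 and 6 months below are assumptions.

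**OS curve level.** Section 2.1.b cites two-year survival after TACE of up to 63%. I take S(24) = 0.63 and assume a constant hazard: λ = −ln(0.63)/24 = 0.01925 per month. Among patients alive at the scan, the curve timed from scan 1 reads 0.63/S(L), with S(L) = exp(−λL).

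| Lag (months) | S(L) | Curve at 24 months | Excess (points) |
|---|---|---|---|
| 1 | 0.981 | 64.2% | 1.2 |
| 2 | 0.962 | 65.5% | 2.5 |
| 4 | 0.926 | 68.0% | 5.0 |
| 6 | 0.891 | 70.7% | 7.7 |

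The life-expectancy exclusion in 3.2 should reduce early deaths. If it halves the first-year hazard with S(24) held at 0.63, the readings are 63.6, 64.2, 65.5 and 66.7%. For scale, the standard error is √(0.63 × 0.37/20) = 10.8 points for 20 patients and √(0.63 × 0.37/10) = 15.3 points for a median-split group of 10.

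**OS comparison.** With a fixed lag, every scanned patient is at risk at every event time, whichever origin is used. The risk sets, Cox hazard ratio and log-rank statistic are therefore identical.

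**PFS if progressed patients are scanned.** This is a simulation with 400,000 patients per cell. The marker is N(0,1) and unrelated to outcome, time to progression is exponential (assumed median 12, 18 or 24 months), death is independent at the OS hazard, and follow-up is censored at 24 months. The value is raised by an assumed 0.5 or 1.0 SD if progression came before the scan. Median-split hazard ratios, where the true value is 1:

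| Median (months) | Shift | L = 2 | L = 4 | L = 6 |
|---|---|---|---|---|
| 12 | 0.5 SD | 1.10 | 1.19 | 1.26 |
| 12 | 1.0 SD | 1.19 | 1.39 | 1.57 |
| 18 | 0.5 SD | 1.09 | 1.15 | 1.22 |
| 18 | 1.0 SD | 1.15 | 1.30 | 1.46 |
| 24 | 0.5 SD | 1.06 | 1.13 | 1.20 |
| 24 | 1.0 SD | 1.12 | 1.25 | 1.39 |

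- At L = 1 month the range is 1.03-1.10.
- If half of the progressed patients are scanned, the range over lags of 2-6 months is 1.04-1.34.
- With no shift it is 0.99-1.01.
- With analysis from the scan date among event-free patients and exact progression dates, it is 0.99-1.01.

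At n = 20 with a 1.0 SD shift, the two-sided log-rank error rate was 5.6-6.9% at 1 month and 6.5-8.0% at 2 months, rising to about 16% in the worst cell (median 12, lag 6). With the fix it was 5.5-7.5%.

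**PFS if progressed patients are not scanned.** The curve then carries guaranteed event-free time. With median time to progression 18 months, the hazard is ln2/18 + 0.01925 = 0.05776 per month and true 24-month PFS is exp(−24 × 0.05776) = 25.0%. The curve reads exp(−0.05776 × (24 − L)) = 28.1, 31.5 and 35.4% at L = 2, 4 and 6.

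**The case against.** The strongest reply is that little depends on this analysis. Aim 1.2.a uses the scan before TACE. Aim 1.2.b concerns response, which 7.3 handles by logistic regression. Later-scan values against OS and PFS appear only in 7.3, which calls the work exploratory. This stands, and it sets the severity.

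The PFS bias also needs facts the plan does not give: that progressed patients are scanned, and that progression moves the marker. Section 2.2.d reports that hypoxic tissue did not correlate with tumor volume in earlier studies, the growth statement in 2.1.a is general biology rather than evidence in embolized tumors, and T/Bmax is a single-pixel maximum rather than a volume. The initial-PET origin for PFS is itself inferred from a sentence about survival. The largest ratios need lags that no section states, and the simulation used exact event times with an ordinary log-rank test, not the planned interval-censored method. All of this stands as a limit on size.

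Two defences fail. Interval censoring deals with six-monthly ascertainment, not with the origin or with who is at risk. The schema's mention of progression sets no scanning rule; if it did stop scanning, guaranteed event-free time would replace the reversed order.

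A reader might also infer that the OS hazard ratios suffer immortal-time bias. The documents do not support that: both median groups must survive to the scan, and no section links scan timing to scan value. Repeat TACE makes timing vary, but variation alone does not bias the comparison.

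**Conclusion.** The point holds as a minor one. The origin in 7.3 does not fit predictors measured at least 1 or 2 months later, and nothing in the plan repairs this.

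For PFS, the null hazard ratio could be about 1.03-1.10 at the scan-2 minimum lag and 1.06-1.19 at the scan-3 minimum. It reaches about 1.4-1.6 only at assumed lags of 4-6 months with the larger assumed shift. These figures rest on the assumed progression rate, on progressed patients being scanned and on the assumed rise in the value; with no rise there is no bias. It would go too far to say that the planned PFS results will be biased.

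For OS, the effect is on the level of the FU1, FU2 and change curves, well within one standard error at the minimum lags. The OS hazard ratio and log-rank test are essentially unaffected unless scan timing is linked to scan value. Baseline-scan models, the response analysis and the primary endpoint are not affected.

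**What to change.** In 7.3, keep the initial-PET origin for baseline values and state that it applies to both OS and PFS. For FU1, FU2 and change values, analyse survival from the date of the scan that supplies the value, or with delayed entry at that date. Include patients alive on that date for OS, and alive and progression-free for PFS. Name one of the two options in advance and apply it to the Cox, Kaplan-Meier/log-rank and interval-censored analyses.

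Set progression status from the dated imaging or clinic record, not from the date of the six-monthly database review. This matters: if progression counts only from the review date, early progressors stay in, and the null hazard ratio remains about 1.06-1.16 at a 2-month lag and 1.12-1.34 at 4 months. Report how many patients had an event or unknown status before each scan. Add a sensitivity analysis that excludes patients whose progression interval spans the scan date.

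The cost is wording plus care in abstracting dates from records already in use; no visits are added. The PFS models lose patients and events: at medians of 12-18 months and lags of 2-6 months, about 13-18 of 20 patients and 9-14 events remain, against 13-16 events as planned. Some bias will persist where the progression date is uncertain.

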### **2.1.b. Use of hypofractionated radiotherapy and trans arterial chemoembolization (TACE)**

Hypoxic cell sensitizers and hypofractionated radiotherapy have been used to circumvent radio-resistance of hypoxic tumors. The latter exerts its effect through activation of the immune system, endothelial cell death and re-oxygenation. High dose hypofractionated radiation is increasingly being used in the treatment of solid tumors, made possible by the availability of sophisticated computing and systems capable of delivering focused radiation with very high fidelity. This treatment has the advantage of ensuring rapid fall off of radiation away from the target, which helps to reduce the incidence of normal tissue complications.

Trans Arterial Chemoembolization (TACE) is another local therapy currently recommended for most unresectable HCC due to clinical results that show improved survival when compared to best supportive care alone. TACE exerts its effect by interrupting arterial supply, predominantly to the center of the tumor (Lo 2002, Llovet 2002). Though up to a 63% survival rate is reported at 2-years following TACE, it is still considered a life-prolonging palliative therapy, as the procedure seldom completely eliminates the tumor. The impact of TACE in inducing tumor hypoxia is not clearly known. Theoretically, TACE triggers expression of proteins associated with tumor progenitor cell differentiation. In a study by Lai et al, the cell hypoxia marker CAIX, and cholangiocytic/progenitor markers CK19 and EpCAM were increasingly expressed in areas of hypoxia within HCC following TACE procedure (Lai 2015).

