A number of strategies are currently used to circumvent TACE induced hypoxia in HCC. These include the addition of hypoxia-activated prodrugs (such as TH-302) or multi-kinase inhibitors (such as Sorafenib) following TACE. At the University of Alabama at Birmingham (UAB), we have adopted a strategy of combining TACE with highly focused hypofractionated radiotherapy (Stereotactic Body Radiotherapy -SBRT). SBRT combined with TACE offers a number of theoretical advantages such as radio-sensitization, spatial targeting and hypoxic targeting, which can potentially improve tumor control. In a study from our institution, Jacob et al observed significantly improved survival rates among HCC patients treated using a combination of TACE-SBRT compared with those treated with TACE alone. This treatment related survival advantage was more pronounced among patients with tumors over 3 cm, implying that inherent or TACE-induced hypoxia is likely a treatment resistance risk factor in larger tumors.

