#### **5.4 Duration of Follow Up.**

Being an imaging only trial, we will not be seeing the patients in nuclear medicine after the last imaging is completed. We will be able to obtain clinical follow-up information from medical records generated at clinic visits and update our data base at 6 month intervals, for two years. Final analysis will take place at the completion of patient accrual.

**5.5. Data Collection.** Treatment selection is based on current clinical practices.

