### **7.2 Sample Size/Accrual Rate**

This is a Phase II study in patients with Hepatocellular Carcinoma (HCC). We propose a sample size of 20 patients for this initial clinical trial because of patient recruitment based on low HCC incident from UAB tumor register data. If the results are promising but inconclusive, they will be used to define a larger multi-center trial. We expect to have a full enrollment in 2 years. From the previous study (Rajendran 2006), a significant hypoxia was identified in 58 patients (79%) in head and neck cancer. The mean

FMISO T/Bmax was 1.6 (range 1.0–3.5) and the mean HV was 40.2 mL (range 0–1092). We expect at least 60% hypoxia/uptake (e.g. TB ratio changes from baseline >1.2) will be identified in HCC patients in this study, thus with a size of 20 patients we will be able to have an accurate estimation of patients who will have undertaken of [F] FMISO with ~ 10% error, and produces a two-sided 95% confidence interval with a width equal to 0.448 for each FMISO PET scan. The size will be also able to evaluate pre-post changes of 1.5 effect size for T/Bmax based on the above published data using one group paired t-test with >80% power at 5% alpha level. Due to the nature of exploratory to generate hypothesis data for future study, the intra correlation between FMISO PET scans within the same subject will not considerate in the sample size consideration this time.

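### The adjusted exploratory Cox and logistic models in section 7.3 have no covariate limit and no sparse-data method for 20 patients, so FMISO effects will tend to be overstated and fits will often be unstable

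*Combined protocol and SAP*

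**What the plan says.** Section 7.2 fixes the size: "We propose a sample size of 20 patients for this initial clinical trial". For the exploratory endpoints, section 7.3 plans Cox regression for overall and progression-free survival and logistic regression for clinical response as yes or no. It asks for hazard and odds ratios with 95% confidence intervals. On adjustment it says "Patient's demographics and other prognosis factors will be adjusted in the model", and then: "The set of prognostic variables considered in the analysis include standard clinical measures (age, tumor-node-metastasis status". HV and T/Bmax enter in separate models because they are highly correlated, and the baseline, follow-up and change values are used one at a time.

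The plan gives no expected number of deaths, progressions or responders, no cap on covariates, no coding for TNM, no list of demographics, and no penalised or exact method. It does label the analysis exploratory because of the small sample.

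The only survival rate in the documents is background, in section 2.1.b: "Though up to a 63% survival rate is reported at 2-years following TACE". The same section reports that an institutional study "observed significantly improved survival rates among HCC patients treated using a combination of TACE-SBRT" compared with TACE alone, without giving a rate.

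On follow-up, section 5.4 says the team will "update our data base at 6 month intervals, for two years", and also that "Final analysis will take place at the completion of patient accrual". The Schema says "patients will be followed for two years or until disease progression".

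**The concern.** Maximum likelihood for Cox and logistic models is biased away from the null when there are few events per fitted term, and a coefficient can run to infinity when a covariate pattern contains no events. Twenty patients and an open-ended adjustment set put these models in that region.

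The estimates are meant to generate hypotheses, and section 7.2 says promising results will be used to define a larger multi-center trial. If an inflated hazard or odds ratio were carried into that design, the trial would be sized for too large an effect. A fit with a diverging covariate also gives an FMISO ratio that is hard to interpret, even when that ratio is itself finite.

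**Working it through.** **The plan's own figures.** Section 7.2 gives a 95% interval width of 0.448 for a proportion of 60% with n = 20. Clopper-Pearson for 12/20 is 0.361 to 0.809, and 0.809 − 0.361 = 0.448, so this reproduces. Its paired t-test claim (effect size 1.5, n = 20) gives power above 0.999, consistent with more than 80%. Neither figure concerns the Cox or logistic models, for which the plan states nothing to reproduce.

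**Deaths.** With two-year survival S and everyone followed for two years, expected deaths are 20 × (1 − S).
- S = 63% (background figure, used here as an assumption): 20 × 0.37 = 7.4, binomial 95% range 3 to 12.
- Assumed S = 75% to 50%: 5 to 10.

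If the analysis is done when accrual closes, with uniform two-year accrual and exponential survival, the expected number is 20 × [1 − (1 − S)/(−ln S)].
- S = 63%: 20 × [1 − 0.37/0.462] = 4.0.
- S = 75% to 50%: 2.6 to 5.6.

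**Deaths per term.** The number of terms is not given, so 4 to 6 is assumed here (one FMISO parameter, age, one or two TNM terms, one or two demographics). At 7 deaths, 7/6 to 7/4 is 1.2 to 1.8 per term. At 4 deaths, 4/6 to 4/4 is 0.7 to 1.0.

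**The other outcomes.** Deaths limit only the overall-survival model. Progression-free survival has its own event count, which the documents do not give. For response, the limit is the smaller of the two outcome groups, at most 10 of 20.

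**Simulation.** There were 1,500 trials of 20 patients per scenario, with a true hazard or odds ratio of 2 per SD of FMISO. The covariates were continuous age and binary terms with prevalences of 20% to 40%, none affecting outcome. Fits were ordinary, unpenalised Cox (right-censored) and logistic models. FMISO counts as diverging when its ratio is above 100 or below 0.01; any coefficient counts when its absolute log value exceeds 8. Inflation is the mean FMISO log estimate among non-diverging fits divided by the true value. CI ratio is the median upper limit over lower limit.

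| Outcome (assumption) | Terms | Inflation | Any coefficient diverges | FMISO diverges | CI ratio |
|---|---|---|---|---|---|
| OS, two years, about 7 deaths | 1 | 1.17 | 0.1% | 0.1% | 5.9 |
| | 3 | 1.31 | 5.0% | 1.2% | 7.4 |
| | 4 | 1.38 | 17.1% | 2.1% | 8.2 |
| | 5 | 1.41 | 27.4% | 4.5% | 10.3 |
| | 6 | 1.57 | 45.9% | 9.3% | 14.3 |
| OS, accrual end, about 4 deaths | 3–6 | 1.30–1.38 | 31–82% | 14–35% | 24 and upward |
| PFS, 13 events assumed | 3–6 | 1.23–1.49 | 0.3–11.8% | under 1% | 4.5–6.4 |
| Response, 30% assumed | 3–6 | 1.37–1.54 | 11–64% | 4–23% | 19–87 |
| Response, 50% assumed | 3–6 | 1.42–1.63 | 3–53% | 3–16% | 14–49 |

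On the ratio scale, a true hazard ratio of 2 at about 7 deaths appears on average as 2^1.31 = 2.5 to 2^1.57 = 3.0. At about 4 deaths the inflation column understates the problem, because the diverging FMISO fits are left out of it.

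A separate simulation with five terms and about 7 deaths gave inflation of about 1.7 and some diverging coefficient in about 25% of fits. The direction is stable; the exact factor depends on the coding.

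**Does the remedy work?** In smaller overall-survival simulations at about 7 deaths, Firth's method with FMISO alone or with one covariate gave inflation between 0.98 and 1.12, with divergence in at most 0.3% of fits. An ordinary Cox fit with one covariate gave 1.28 and 11%. Firth was not simulated here for progression-free survival or response.

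**The case against.** The strongest reply is that the plan already calls this work exploratory, cites the small sample and leaves confirmation to future studies. It also keeps the models smaller than they might be by entering HV and T/Bmax separately and each time point individually, and it includes unadjusted analyses (Kaplan-Meier curves with log-rank tests by median split, and ROC analysis). All of this is true and limits the consequence. It changes no fitting method, however, and the adjusted ratios with confidence intervals are still to be reported.

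Several stronger readings are tempting, and the documents do not support them:
- A reader might infer that all these models rest on about 7 deaths. That count applies to overall survival only.
- A reader might take 63% as a planning value. It is an upper background figure for TACE. Better survival with TACE-SBRT, analysis at accrual end, or stopping follow-up at progression would each lower the deaths captured.
- A reader might infer that FMISO effects will be inflated or inestimable in this trial. Inflation is an average tendency given a real effect, not a statement about any one estimate. At about 7 deaths FMISO itself diverges in about 1% to 9% of fits; the commoner failure is a covariate.

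Two further objections stand. The number and coding of covariates are assumed, because the plan gives neither. The simulation used ordinary right-censored Cox fits, whereas section 7.3 also mentions an interval-censored survival analysis, to which these figures and the Firth remedy do not directly apply.

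**Conclusion.** The concern holds for the adjusted exploratory models. If the background survival figure is assumed, 3 to 6 terms are fitted and the true hazard ratio is 2 per SD, ordinary maximum likelihood at about 7 deaths tends to inflate the FMISO log hazard ratio by about 1.3 to 1.6 times, against 1.17 unadjusted. Some coefficient diverges in about 5% to 46% of fits. Adjusted logistic log odds ratios are inflated by about 1.4 to 1.6 times at assumed response rates of 30% to 50%, against 1.22 to 1.26 unadjusted. Progression-free survival is less affected if it has more events, but at an assumed 13 events the inflation is still 1.23 to 1.49.

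The sizes rest on assumed covariates, prevalences, effect size and event rates. The primary endpoint (change in HV and T/Bmax) is unaffected, and nothing here shows that the trial's main results are at risk.

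**What to change.** In section 7.3, for the Cox and logistic models:
1. Fit all of them with Firth's penalised likelihood and give profile-likelihood 95% confidence intervals.
2. Report the unadjusted FMISO estimate alongside models that add at most one covariate at a time, with the covariates named in advance (for example age or TNM stage, with its coding). The one-covariate models keep Aim 1.2.a, on independent prediction, in view; an unadjusted estimate alone would not address it.
3. Describe all of these estimates as hypothesis-generating.

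The interval-censored analysis stays as planned.

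The cost is a few sentences of SAP text and a model option in the software already named. The real downside is less adjustment for confounding: independent prediction can be examined only one covariate at a time. Intervals also stay wide. Even the unadjusted ordinary fits had an upper-to-lower limit ratio of about 6 for overall survival and 10 to 12 for response, and no choice of method makes 20 patients precise.
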